## List of abbreviations

AE	Adverse Event
ADR	Adverse Drug Reaction
BMI	Body Mass Index
CRF	Case Report Form
eCRF	Electronic Case Report Form
DM	Diabetes Mellitus
EDC	Electronic Data Capture
EMA	European Medicines Agency
GPP	Good Pharmacoepidemiology Practice
GW	Gestation Week
IEC	Independent Ethics Committee
IRB	Institutional Review Board
LAR	Legally Acceptable Representative
PSUR	Periodic Safety Update Report
RDS	Respiratory Distress Syndrome
SAE	Serious Adverse Event
T1DM	Type 1 Diabetes Mellitus
T2DM	Type 2 Diabetes Mellitus

## Glossary

Congenital malformation	A morphological defect of an organ, part of an organ, or larger region of the body resulting from an intrinsically abnormal developmental process
Early foetal death	The death of a foetus before completion of 22 gestational weeks (GW)
Ectopic pregnancy	A pregnancy that occurs outside the uterus
Late foetal death	The death of a foetus after the completion of 22 gestational weeks (GW) including stillbirth
Foetal macrosomia	Birth weight above 4 kg
Large-for gestational age	Live born infant with birth weight > 90th percentile for gestational age and sex according to local reference
Major malformations	A life-threatening structural anomaly or an abnormality likely to cause significant impairment of health or functional capacity and which needs medical or surgical treatment. Examples are abnormalities likely to lead to serious handicap or likely to lead to major cosmetic defects (e.g. cleft lip) and which may require major surgery to repair (e.g. atrial septal defect or ventricular septal defect)
Major hypoglycaemia	A hypoglycaemic episode where the patient is not able to treat him/herself and where oral carbohydrates, glucagon or intravenous glucose has to be administered to the patient by another person because of severe central nervous system dysfunction
Minor malformations	Structural anomaly not likely to cause any medical or cosmetic problems
Neonatal death	Death of an infant between 7 days and 28 completed days after delivery
Perinatal death	Death of a foetus/infant between $\geq 22$ completed GWs and $< 1$ completed week after delivery
Pregnancy outcome	The end products of pregnancy which include three main categories: foetal death, spontaneous abortion, and live birth
Pre-term delivery	Delivery before 37 completed gestational weeks
Pre-eclampsia	A condition in pregnancy characterised by new onset of abrupt hypertension (140/90 millimetres of mercury (mm Hg) or greater

documented on two occasions, at least 6 hours but no more than 7 days apart), and albuminuria

Spontaneous abortion      A naturally occurring termination of a pregnancy before 22 completed gestation weeks. Also called miscarriage

## 1 Summary

The overall objective of the Diabetes Pregnancy Registry is to monitor and assess the safety of Levemir® use in pregnant women with diabetes mellitus (DM), and to monitor their infants at 1 month and 1 year of age. As a part of the observational data collection, equivalent data will be collected from pregnant women with DM treated with other injectable antidiabetic treatment regimens and their infants until 1 year of age.

A change in type or brand of basal insulin after baseline visit will lead to exclusion from the primary and secondary endpoint analysis, but not from the registry itself. For the primary and secondary objectives comparisons will only be made between women treated with Levemir® and women treated with other basal insulin regimens, who have not changed basal insulin product 4 weeks prior to conception and until delivery/pregnancy termination.

### **PRIMARY OBJECTIVE:**

#### *Pregnancy outcome*

Comparison of the proportion of pregnancies in pregnant women who have completed 22 weeks of pregnancy and treated with Levemir® to pregnant women who have completed 22 weeks of pregnancy and treated with other basal insulin regimens which results in none of the following events:

- Major congenital malformations
- Perinatal death
- Neonatal death

Assessed at up to 4 weeks after delivery

### **KEY SECONDARY OBJECTIVES:**

#### *Maternal*

Comparison of the following adverse events and abnormal metabolic control in pregnant women treated with Levemir® to pregnant women treated with other basal insulin regimens:

- Incidence of major hypoglycaemic events during the pregnancy period
- Development of pre-eclampsia during pregnancy

### ***Pregnancy outcome***

Comparison of pregnancy outcomes in women treated with Levemir® to those treated with other basal insulin regimens with respect to:

- Pre-term delivery
- Spontaneous abortion
- Perinatal death
- Neonatal death

### ***Infants at the age of 1 year***

Comparison of, at 1 year of age, the growth and health of infants born to women treated with Levemir® to those born to women treated with other basal insulin regimens.

### **PRIMARY ENDPOINT:**

Comparison of the proportion of pregnancies in pregnant women who have completed 22 weeks of pregnancy and treated with Levemir® to pregnant women who have completed 22 weeks of pregnancy and treated with other basal insulin regimens which results in none of the following events:

- Major congenital malformations
- Perinatal death
- Neonatal death

Assessed at up to 4 weeks after delivery

### **KEY SECONDARY ENDPOINTS:**

#### **Maternal endpoints**

- Incidence of major hypoglycaemia during pregnancy
- Proportion of pregnancies complicated by pre-eclampsia during pregnancy

### **Pregnancy outcome endpoints**

- Proportion of pregnancies resulting in perinatal death assessed 1 week after delivery
- Proportion of pregnancies resulting in neonatal death assessed 4 weeks after delivery
- Proportion of pregnancies resulting in spontaneous abortion assessed at pregnancy termination
- Proportion of pregnancies resulting in pre-term delivery assessed at delivery

### **Infant endpoints at 1 year of age**

- Height at the age of 1 year
- Weight at the age of 1 year
- Proportion with changes (progression/regression) of major congenital malformations

For pregnancies with multiple foetuses each foetus will be counted individually for the primary endpoint, the other pregnancy outcome endpoints, and the infant endpoints at 1 year of age.

### **STUDY DESIGN:**

This international, prospective, non-interventional, multi-centre cohort study will monitor and assess the safety of Levemir® use during pregnancy as well as monitor the health status of the infants at 1 month and 1 year of age. The same parameters will also be monitored and assessed for other injectable antidiabetic treatment regimens used during pregnancy. The study period includes the gestation periods of the pregnant women and the follow-up of the infants at 1 month and 1 year of age. The Diabetes Pregnancy Registry has a planned recruitment period of 5 years.

### **STUDY POPULATION:**

Women with DM, who are pregnant and treated with Levemir® or other injectable antidiabetic treatment regimens, and who have not changed basal insulin or other injectable antidiabetic treatment product (for those not treated with basal insulin) 4 weeks prior to and following conception will be included in the Diabetes Pregnancy Registry.

For the statistical analyses only women treated with basal insulin will be included. The group of women treated with Levemir® will be compared to the group of women treated with other basal insulins.

### **Inclusion criteria**

1. Informed consent obtained before any data collection
2. Woman with a positive pregnancy test
3. Diabetes mellitus type 1 or 2, diagnosed prior to conception
4. Currently treated with Levemir® or other injectable antidiabetic treatment(s)
5. Unchanged basal insulin or other injectable antidiabetic treatment product (for those not treated with basal insulin) 4 weeks prior to and following conception

### **Exclusion criteria**

Women who have been pregnant for more than 16 weeks at baseline visit will be excluded from the study.

### **ASSESSMENTS:**

All adverse drug reactions (ADRs) and serious adverse events (SAEs) in pregnant women treated with any injectable antidiabetic treatment regimens, as well as in their off-spring until 1 year of age, should be reported. In addition, pre-eclampsia and major hypoglycaemic events in the pregnant women should be reported regardless of causal relationship and seriousness criteria.

### **STUDY PRODUCT(S):**

Levemir® and other injectable antidiabetic treatment regimens.

## 2 Flow chart

Flow chart of visits and standard routine procedures.

Visit	Baseline visit	Standard routine visits	Delivery visit	Follow-up of the infant(s)	Follow-up of the infant(s)
Time of visit	≤ 16 weeks pregnant	Any time during pregnancy	Delivery	1 month after delivery	1 year after delivery
Visit window				+ 1 month	+ 4 months
Informed consent	x				
Incl. /excl. criteria	x				
Demographics	x				
Obstetric history	x				
Maternal medical history	x				
Maternal diabetes history	x				
Current antidiabetic treatment	x	x	x		
Concomitant illness	x				
Concomitant medication	x	x	x		
Height 	x		x	x	x
Weight 	x	x	x	x	x
Vital signs	x	x			
Current pregnancy information	x				
HbA 1c	x 	x	x		
Major hypoglycaemia		x	x		

Pre-eclampsia		x	x		
ADRs and SAEs 		x	x	x	x
Delivery and complications			x		
Pregnancy outcome			x		
Neonatal assessments			x		
Foetal assessments 			x		
Neonatal death				x	
Congenital malformations not detected at delivery				x	
Lactation				x	x
Diabetes					x
Changes of major congenital malformations					x

1. Height and weight of the mother during pregnancy and of the infant(s) at delivery, 1 month and 1 year follow-up
2. HbA1c measured ≤ 16 weeks prior to baseline visit is acceptable as baseline visit data (see section [8.1.1](#))
3. Relevant ADR's and SAE's according to protocol section [9](#)
4. Foetal assessments in case of early termination of pregnancy, perinatal and neonatal death
5. Preferably data from one standard routine visit per month should be entered into the eCRF irrespectively of the number of visits performed

### 3 Introduction

In this document physician refers to the individual overall responsible for the conduct of the non-interventional study at a study site.

#### 3.1 Basic information

The use of insulin analogues has increased significantly in the treatment of both type 1 and type 2 diabetes mellitus (T1DM and T2DM, respectively). Insulin analogues are used in pregnant women with diabetes, as this group has a particular requirement for the safe and efficacious treatment that insulin analogues can deliver. As pregnancy in women with DM is associated with an increased risk of complications for both the mother and the foetus/new-born especially if glycaemic control is outside the target, and as the treatment needs to be adjusted during pregnancy, it is considered a medical challenge to ensure that these women receive the most optimal glycaemic control without inducing hypoglycaemia. If pregnant women receive optimal treatment, it will both increase their own well-being and reduce the overall risk of diabetes complications and pregnancy complications both for the mother and the child. Complications associated most frequently with pregnancies in women with DM include the following :

- Major hypoglycaemia
- Progression of maternal diabetic complications
- Spontaneous abortion
- Pre-eclampsia and pre-term delivery
- Perinatal and neonatal death
- Congenital malformations
- Foetal macrosomia

During recent decades, pregnancy outcomes in women with DM have improved considerably. Hypo- and hyperglycaemia remain, however, a major challenge in the treatment of pregnant women with DM. The proportion of pregnant women reporting major hypoglycaemic episodes that require third party help is as high as 71% . Of these, 33–41% of the episodes additionally require parenteral glucose or glucagon.

The rate of pre-eclampsia in pregnancies in women with DM increases with advanced maternal age, poor glycaemic control and baseline proteinuria . The literature is inconsistent in particular with respect to the rate and severity of pre-eclampsia, but the minimum risk reported in women with DM is 10% .

The most common organs affected by malformations are the central nervous system, heart, skeleton, kidneys, gastro-intestinal tract and lungs. The prevalence of major congenital anomalies in infants of women with DM was 4.5% in a population-based study in England, Wales and Northern Ireland

[11](#) and the results are in line with results from a nationwide prospective Norwegian study from 2010 [12](#). In addition, infants of women with DM are 5 times more likely to be stillborn and 3 times more likely to die in their first month of life (neonatal death) compared with those of mothers without DM [11](#). The perinatal death risk is approximately 3% and the neonatal death risk is 0.9% [11](#) and comparable with rates from other European countries [11,13-17](#). Finally, foetal macrosomia is reported to occur in 25–30% and in some studies in more than 40% of the new-borns to mothers with DM [5,7](#).

Pregnant women with DM and with good metabolic control are not more likely than non-diabetic women to lose a pregnancy. This is in contrast to a risk of 15–26% of having a spontaneous abortion in the first trimester for diabetic women who have elevated blood glucose levels [3,8,9](#). As increased perinatal and neonatal death, morbidity and a 2–5-fold increase in congenital anomalies compared with the general population are reported in pregnant women with DM [2](#), further data on the effects of treatment on pregnant women with DM are needed.

Levemir® was approved for treatment of pregnant women with DM in the EU in 2011 [18](#).

### 3.2 Rationale for the study

As prospective data on the effects of different insulin treatment regimens in general are limited and as no long-term prospective epidemiological studies examining safety in pregnant women with DM and pregnancy outcomes have been conducted, a diabetes pregnancy registry including such prospective data is highly warranted.

Novo Nordisk A/S will establish an international Diabetes Pregnancy Registry to monitor the safety of the use of Levemir® and other injectable antidiabetic treatment regimens in pregnant women during the gestational period and to monitor their infants at the age of 1 year. The present registry constitutes a unique opportunity for large-scale data collection that will allow comparisons and analysis between the various insulin treatment regimens in pregnant women with DM.

All data collection and statistical analysis will be done in accordance with global and local regulations and legal data protections requirements.

## 4 Objectives and endpoints

### 4.1 Objective(s)

The overall objective of the Diabetes Pregnancy Registry is to monitor and assess the safety of Levemir® use in pregnant women with DM, and to monitor their infants at 1 month and at 1 year of age. As a part of the observational data collection, equivalent data will be collected from pregnant women with DM treated with other injectable antidiabetic treatment regimens, and their infants at 1 month and at 1 year of age.

For the primary and secondary objectives comparisons will only be made between women treated with Levemir® and women treated with other basal insulin regimens, who have not changed basal insulin product 4 weeks prior to conception and until delivery/pregnancy termination.

#### 4.1.1 Primary objective

##### *Pregnancy outcome*

Comparison of the proportion of pregnancies in pregnant women who have completed 22 weeks of pregnancy and treated with Levemir® to pregnant women who have completed 22 weeks of pregnancy and treated with other basal insulin regimens which results in none of the following events:

- Major congenital malformations
- Perinatal death
- Neonatal death

Assessed at up to 4 weeks after delivery.

#### 4.1.2 Secondary objective

##### *Maternal*

Comparison of the following adverse events and abnormal metabolic control in pregnant women treated with Levemir® to pregnant women treated with other basal insulin regimens:

- Incidence of major hypoglycaemic events during the pregnancy period
- Development of pre-eclampsia during pregnancy
- Metabolic control measured as HbA1c during pregnancy

##### *Pregnancy outcome*

Comparison of pregnancy outcomes in women treated with Levemir® to those treated with other basal insulin regimens with respect to:

- Foetal macrosomia
- Large-for gestational age
- Pre-term delivery
- Spontaneous abortion
- Induced abortion due to major congenital malformations (by organ)
- Perinatal death
- Neonatal death
- Live birth with major congenital malformations(by organ)
- Live birth with minor congenital malformations(by organ)

### *Infants at the age of 1 year*

Comparison of, at 1 year of age, the growth and health of infants born to women treated with Levemir® to those born to women treated with other basal insulin regimens.

## **4.2 Endpoints**

### **4.2.1 Primary endpoints**

Comparison of the proportion of pregnancies in pregnant women who have completed 22 weeks of pregnancy and treated with Levemir® to pregnant women who have completed 22 weeks of pregnancy and treated with other basal insulin regimens resulting in none of the following events:

- Major congenital malformations
- Perinatal death
- Neonatal death

Assessed at up to 4 weeks after delivery.

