#### 4.2.2.2 Pregnancy outcome endpoints

- Proportion of pregnancies resulting in perinatal death assessed at 1 week after delivery
- Proportion of pregnancies resulting in neonatal death assessed at 4 weeks after delivery
- Proportion of pregnancies resulting in live birth with major congenital malformations and by organ assessed at delivery
- Proportion of pregnancies resulting in live birth with minor congenital malformations and by organ assessed at delivery
- Proportion of induced abortions due to major congenital malformations and by organ assessed at delivery
- Proportion of pregnancies resulting in spontaneous abortion assessed at pregnancy termination
- Proportion of pregnancies resulting in live birth with foetal macrosomia assessed at delivery
- Proportion of pregnancies resulting in live born infants with birth weight > 90th percentile for gestational age and sex (local reference) assessed at delivery
- Proportion of pregnancies resulting in pre-term delivery assessed at delivery

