### 6.1 Number of patients to be studied

Estimated number of patients to be included during the recruitment period: minimum: 2,037

Recruitment will close once it is secured that 611 patients treated with Levemir® are eligible for the primary analysis.

Based on sample size calculations (Section 14) the number of pregnancies needed for the primary endpoint calculations is 1,222 pregnancies with information on the primary endpoint pregnancy outcomes:

- perinatal death
- neonatal death
- liveborn infant with 1 month follow up (irrespective if there is a malformation or not)

Liveborn infants will be followed up until 1 year with the aim of collecting data for the secondary endpoints.

It is expected that approximately 60% of the included pregnancies will be fulfilling the criteria for primary endpoint calculations, as 40 % are assumed to be excluded or used for secondary endpoints. These 40% of subjects are assumed to consist of subjects who experience one or more of the following: abortion (spontaneous or induced), change in basal insulin treatment, treatment with other antidiabetic treatment regimens, or lost to follow-up.

Therefore, it is calculated that a minimum of  $(1,222/60*100)$  2,037 patients are to be included in the study.

Note that the study plans to include a minimum of 2,037 patients treated with injectable antidiabetic treatment regimens, but that only women treated with Levemir® and other basal insulins will be included in the primary analyses.

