### **8.3.12 Foetal assessments (in case of early termination of pregnancy, early foetal death and perinatal death) and neonatal death**

The following details regarding foetal/infant death will be recorded at the pregnancy outcome page in the case report form (CRF):

- Induced abortion (interruption of a living pregnancy < 22 completed weeks)
- Spontaneous abortion
- Ectopic pregnancy
- Perinatal death
- Neonatal death
- GW at termination
- Malformations (y/n)
- If yes, minor/major malformations by organ
- Other relevant information (e.g. autopsy) (y/n)

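### The primary endpoint does not count major malformations ended by induced abortion before 22 weeks, no planned analysis adds them back, and section 6.1 sets a 1-month condition that 4.2.1 and 13 do not

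*Protocol*

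**What the plan says.** Section 4.2.1 of the protocol sets the primary endpoint as a "Comparison of the proportion of pregnancies in pregnant women who have completed 22 weeks of pregnancy" that end without major malformation, perinatal death or neonatal death, "Assessed at up to 4 weeks after delivery". The Summary and section 4.1.1 carry the same 22-week restriction.

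Section 8.3.12 lists "Induced abortion (interruption of a living pregnancy < 22 completed weeks") among the outcomes to be recorded and asks about malformations in these cases: "If yes, minor/major malformations by organ". Section 4.2.2.2 reports such cases as a secondary endpoint: "Proportion of induced abortions due to major congenital malformations and by organ assessed at delivery". It also has "Proportion of pregnancies resulting in live birth with major congenital malformations and by organ assessed at delivery".

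Section 6.1 lists the outcomes that supply primary-endpoint information: perinatal death, neonatal death, or a "liveborn infant with 1 month follow up (irrespective if there is a malformation or not"). About 40% of enrolled pregnancies are expected not to qualify, because of "abortion (spontaneous or induced), change in basal insulin treatment, treatment with other antidiabetic treatment regimens, or lost to follow-up".

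Section 13 defines the analysis set by unchanged basal insulin only. It states neither a 22-week nor a 1-month condition. Section 14.4 analyses all endpoints on that set.

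**The concern.** Two selection rules act on the outcome itself.

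The first is the 22-week limit. A major malformation in a pregnancy terminated at 21 weeks leaves both numerator and denominator; the same malformation in a pregnancy that has completed 22 weeks is an event. Whether it counts depends on when it is detected and what is then decided. Those may vary with site, country or type of diabetes, and so with the insulin used.

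The second is the rule in section 6.1. Malformations are recorded at the delivery visit (8.1.3.2 and 8.3.11). An infant with a major malformation recorded then has already met the endpoint, but without the 1-month contact it fits none of the three categories in 6.1. Follow-up to 1 month is needed only to call a pregnancy event-free.

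This is a post-authorisation safety study, and a null primary result will be read as reassurance about malformations. It should be clear which malformations that result covers.

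**Working it through.** **The plan's own figures.**
- Composite event-free proportion (14.2): 0.955 × 0.97 × 0.991 = 0.918.
- Enrolment (14.3): 1,222 / 0.60 = 2,037.
- The 1,222 reproduces: with 611 per group and 93.5% versus 97.0% event-free, the exact power of the two-sided 5% Fisher test is 79.9%.
- These figures hold, and the present point does not depend on them.

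**Inputs from the protocol.** Malformation prevalence 4.5% (14.2, from 3.1, where it is a prevalence in infants); observed event-free proportion 97.3%, so 2.7% with an event (14.3); target difference 3.5 points; 611 per group. The protocol gives no number of terminations before 22 weeks and no loss before 1 month, so the fractions below are assumptions.

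**1. False difference from unequal early termination.** Let the true malformation proportion be 4.5% in both groups, and let a fraction s of affected pregnancies end before 22 weeks. The counted proportion is 0.045(1 − s) / (1 − 0.045s).

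| s, group A | s, group B | Counted A | Counted B | False difference |
|---|---|---|---|---|
| 10% | 10% | 4.07% | 4.07% | 0 |
| 10% | 20% | 4.07% | 3.63% | 0.44 points |
| 10% | 30% | 4.07% | 3.19% | 0.88 points |
| 10% | 40% | 4.07% | 2.75% | 1.32 points |

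The last row is 1.32 / 3.5 = 38% of the target difference. Equal fractions give no false difference.

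**2. Events outside the primary count.** At 2.7%, a group of 611 has 16.5 events. If terminations with a major malformation equal t of 611, the event proportion with them included is (16.5 + 611t) / (611 + 611t):
- t = 0.5%: 3.1 added, 3.2%
- t = 1%: 6.1 added, 3.7%
- t = 1.5%: 9.2 added, 4.1%
- t = 2%: 12.2 added, 4.6%

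**3. The 1-month condition.** If a fraction L of live births misses the 1-month contact and m have a major malformation recorded at birth, the known malformations dropped per 611 counted are 611 × L/(1 − L) × m. With L = 2% and m = 1.5% this is 0.2; with L = 15% and m = 4.5% it is 4.9.

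**4. Why the denominator must match.** Keeping known events while still dropping event-free infants without follow-up inflates the proportion to m / (m + (1 − m)(1 − L)). With m = 2.7% and L = 10%: 0.027 / (0.027 + 0.973 × 0.90) = 2.99%.

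**5. Sections side by side.** Section 4.2.1 has the 22-week limit and no 1-month condition; 6.1 has the 1-month condition; 13 has neither. They do not yield one denominator.

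**The case against.** The 22-week limit is a deliberate choice, stated consistently. Terminations for malformation are a named secondary objective and endpoint. Section 14.4 applies the same Fisher comparison to them, with similar logistic models, and induced abortions must be reported as serious adverse events. The adjusted primary model lists study site and type of diabetes, and sections 5.2 and 5.4 describe routine procedures as similar across sites. The 1-month condition stands only in a sample-size section, and live births with a major malformation at delivery are compared without it in 4.2.2.2.

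Most of this stands, and it rules out three stronger readings that a reader might draw:
- **That a malformation signal showing up as terminations would go unseen.** It would not: terminations for malformation have their own between-group test.
- **That every termination for malformation is lost, or that the most severe malformations are the ones removed.** The label of induced abortion is confined to less than 22 weeks, a foetal death from 22 completed weeks counts as perinatal death, and nothing in the protocol documents severity.
- **That the result favours one insulin.** The protocol gives no basis for a direction.

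What the objection does not answer is narrower. Adjustment can reduce bias that runs through site or type of diabetes, but it does not return removed events or cover other differences. The termination endpoint is absent from the key secondary list in the Summary, and its wording leaves its denominator open. No stated analysis gives total major malformations across terminated and continuing pregnancies. A statistical analysis plan may settle the missing 1-month contacts, but the conflict between 6.1 and 13 is in the protocol itself.

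**Conclusion.** The point holds in limited form. The primary endpoint leaves out major malformations ended by induced abortion before 22 weeks, and no planned analysis combines them with those in continuing pregnancies. The primary comparison is biased if such terminations differ between the groups beyond the adjusted covariates. The protocol does not allow size or direction to be computed. The 1.3-point figure needs a 10% versus 40% split, and it applies 4.5%, a prevalence in infants, as if it were the rate before any termination. It shows what could happen, not what to expect.

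The 1-month condition is an inconsistency between 6.1 and sections 4.2.1 and 13. Its effect is smaller, about 0.2 to 5 known malformations per group on the assumed ranges, and it distorts the comparison between insulins only if loss differs by group. Both matter because only about 16 events per group are expected. They should be fixed; neither invalidates the planned analysis.

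**What to change.** (a) Reconcile 6.1 with 4.2.1 and 13. Count any major malformation recorded up to 4 weeks after delivery as an event, whether or not the 1-month contact took place. Keep all births from 22 completed weeks with a delivery assessment in the denominator, and add a sensitivity analysis for infants whose 1-month status is missing.

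(b) Keep the 22-week primary analysis. In 14.4, pre-specify a supportive analysis with the same Fisher and logistic comparisons that adds induced abortions with a recorded major malformation to numerator and denominator, reported beside the primary result. Define these by the recorded malformation, because 8.3.12 does not list the reason for the abortion.

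The cost is wording in four sections plus one supportive and one sensitivity analysis, with no new data. Malformations in early terminations are less completely ascertained, and terminations before enrolment, which may be as late as 16 weeks, are not seen. On the range for t above, the event-free proportion would be 95.4% to 96.8%, above the 93.5% at which 14.3 calls 1,222 sufficient. That criterion reproduces only with the 3.5 points as an increase. For a decrease, normal-approximation power with 611 per group falls from 84% (97.3% versus 93.8%) to 70% (95.3% versus 91.8%), which is acceptable for a supportive analysis.
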